7.2. Efficacy Hypotheses

The primary efficacy analysis is the comparison of ORR at Day 28 between the 2 treatment groups. The following statistical hypotheses will be tested to address the primary efficacy objective:

$$H_0: ORR_{itacitinib} = ORR_{pbo} \text{ versus } H_1: ORR_{itacitinib} > ORR_{pbo}$$

where $ORR_{itacitinib}$ and ORR_{pbo} are the ORRs at Day 28 in the itacitinib and placebo groups, respectively. The CMH chi-square test, stratified by the randomization stratification factor (ie, standard risk and high risk), will be used to compare ORR between the 2 treatment groups, at the 1-sided 2.5% level of significance.

For the primary efficacy analyses, Day 28 ORR, as well as ORR for scheduled visits at Days 14, 56, 100, and 180, if available, will be used; if a scheduled assessment is not available but an unscheduled visit is available (within 3 days of the scheduled date), then the unscheduled assessment closest to the scheduled date will be used.

For summary analyses over time, analysis visits are defined Section 4.1.5, where analysis visits will be used in both tables and figures. The listings will include all collected data from the eCRF regardless of whether the visits are scheduled or unscheduled.

7.3. Analysis of the Primary Efficacy Endpoint

For all of the following regression analyses specified, regardless of logistic regression, Cox regression, or cause-specific hazard/subdistribution hazard regression in competing-risks analyses, the covariates in the final model can differ from what is specified, depending on the unblinded data.

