7.3.1.2. Sensitivity Analyses for Day 28 Overall Response Rate

Sensitivity analyses for Day 28 ORR will consist of the following:

- Stratified CMH test for Day 28 ORR in the full and per-protocol analysis sets
- Logistic regression method with both treatment group and baseline GVHD risk status as cofactors in the model for the efficacy population
- Separate CMH test by baseline GVHD risk status

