7.4.2. Survival Analyses of Nonrelapse Mortality

Time to death due to causes other than malignancy relapse (NRM) will be analyzed according to the randomized treatment group and strata assigned at randomization.

The hazard ratio of itacitinib relative to placebo overall [REDACTED] will be calculated, along with its 95% CI, using a stratified Cox model.

Stratified log-rank test will also be used to test survival curve of NRM in the treatment group relative to placebo group using the FAS.

Subgroup KM analyses of NRM will also be conducted by Day 28 response status [REDACTED].

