7.4.3. Competing-Risks Analyses of Nonrelapse Mortality

In the literature, analyzing NRM is normally conducted in the context of a competing-risks situation. Time from randomization to first occurrence of NRM or competing event is observed and used for analysis; otherwise, the subject is censored. Nonrelapse mortality and a competing-risk event are mutually exclusive. This is because a subject either dies due to malignancy relapse, dies due to an event other than malignancy relapse, or is censored at last follow-up. There are 2 types of competing-risks analyses:

- I: Time to NRM competing with time to malignancy relapse
Time to first occurrence of either death due to reasons other than malignancy relapse (NRM) or malignancy relapse is defined as an event of interest and competing risk event, respectively. Subjects without an event (neither event of interest nor competing event) will be censored at the date of study withdrawal or date of last contact before or on the cutoff date, whichever is the earlier.
- II: Time to NRM competing with time to death due to malignancy relapse
Time to first occurrence of either death due to reasons other than malignancy relapse (NRM) or death due to malignancy relapse is defined as an event of interest and competing risk event, respectively. Subjects without an event (neither event of interest nor competing event) will be censored at the date of study withdrawal or date of last contact before or on the cutoff date, whichever is the earlier.

For each of the competing-risks analyses (ie, I and II), there are 2 ways of modeling conducted in this study. The first one is cause-specific hazard modeling and the second one is subdistribution hazard modeling.

In cause-specific hazard modeling, competing events will be censored, and a stratified log-rank test [REDACTED] will be used to test 2 KM curves with KMC estimate equals 1 minus KM estimate. In cause-specific hazard modeling, stratified Cox regression model [REDACTED] with a cofactor of treatment group will be used to estimate cause-specific hazard ratio (itacitinib vs placebo) and 95% CI.

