In subdistribution hazard modeling, competing-risk events will be considered to remain in the risk set as described by Gray (1988). Stratified Gray's test [REDACTED] will be used to test equality of 2 cumulative incidence curves. Cumulative incidence function at Day 180 (SE) will be estimated. Stratified subdistribution hazard regression (Fine and Gray 1999) with cofactor of treatment group (itacitinib vs placebo) will be performed, and subdistribution hazard ratio (95% CI) on treatment effect (itacitinib vs placebo) will be estimated.

Cumulative incidence curve for each competing-risk analysis will be plotted overall by Day 28 response status [REDACTED]

7.4.4. Overall Response Rate at Days 14, 56, 100, and 180

Similar to Day 28 ORR, ORR at Days 14, 56, 100, and 180, respectively, is defined as the proportion of subjects demonstrating a CR, VGPR, or PR at a defined analysis visit/window (ie, ± 3 days of scheduled visit date).

The ORR on Days 14, 56, 100, and 180 will be estimated with a 95% CI. The proportion of responders will be estimated with 95% CIs. Confidence intervals will be calculated based on the exact method for binomial distributions. Summary statistics will be provided.

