APPENDIX A. STATISTICAL MODELS FOR EFFICACY ANALYSES

Analysis for Overall Response

Cochran-Mantel-Haenszel test

The null hypothesis of equality of response rate in the 2 treatment groups will be tested against 1-sided alternative. The statistical hypotheses are:

$$H_0: \text{ORR}_{\text{trt}} \leq \text{ORR}_{\text{pbo}} \text{ versus } H_1: \text{ORR}_{\text{trt}} > \text{ORR}_{\text{pbo}}$$

where ORR_{trt} is the probability of response in treatment group and ORR_{pbo} is the probability of response in placebo group. The CMH chi-square test X2CMH (implemented again via SAS procedure FREQ with CMH option in the TABLES statement) will be used to test the difference in response rates between the treatment groups. The p-value corresponding to the CMH test for “general association” will be used, which follows a Chi-square distribution with 1 degree of freedom.

If the sampling assumptions for chi-square test is not met, the exact CMH test will be used (implemented via SAS procedure MULTTEST). The test is performed by running a stratified version of the Cochran-Armitage permutation test (Armitage et al 1969). In studies with stratified randomization, the chi-square approximation is considered appropriate for the X2CMH statistics if the rule of Mantel and Fleiss (1980) is satisfied.

Logistic Regression

Odds ratio will be used as a measure of association between treatment and response. The odds ratio will be derived from the logistic regression model (implemented using SAS procedure LOGISTIC, with both treatment and stratification factor specified as an explanatory variable in the CLASS statement), which allows for including not only the stratification factor but also for adjustments for other covariates (both categorical and continuous). The odds ratio will be presented with 95% Wald confidence limits.

In cases where an exact test has been used to compare response rates, the odds ratio should be determined using exact logistic regression, and the odds ratio presented with exact 95% confidence limits. In these cases, SAS PROC LOGISTIC with EXACTONLY option will be used.

Analyses for Survival Data

Analyses for Survival Data in this section use OS as an example.

Stratified Log-Rank Test

The null hypothesis stating that OS distributions of the 2 treatment groups are equivalent will be tested against 1-sided alternative

Assuming proportional hazards for OS, the following statistical hypotheses will be tested:

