$$H_{02}: \theta_2 \geq 1 \text{ versus } H_{A2}: \theta_2 < 1$$

where θ_2 is the OS hazard ratio (treatment versus placebo). The analysis to test these hypotheses will consist of a stratified log-rank test at an overall 1-sided 2.5% level of significance. The stratification will be based on the randomization stratification factors (ie, aGVHD high vs standard).

The stratified log-rank test adjusting for the strata used in the randomization will be implemented as follows: In each of the K strata separately, the LIFETEST procedure with **STRATA** statement including only the treatment group variable and with the TIME statement will be used to obtain the rank statistic S_k and variance $\text{var}(S_k)$ where $k=1, 2, \dots, K$. The final test statistics will then be reconstructed as follows:

$Z = [S_1 + \dots + S_K] / \sqrt{[\text{var}(S_1) + \dots + \text{var}(S_k)]}$. One-sided P-value will be obtained from the standard normal distribution using the Z statistic.

(One-sided will be obtained using Z statistic / Two-sided p-value will be obtained using Z^2 statistic.)

Kaplan-Meier Estimates

An estimate of the OS survival function in each treatment group at distinct event times will be constructed using KM (product-limit) method as implemented in PROC LIFETEST with METHOD=KM option. The PROC LIFETEST statement will use the option CONFTYPE=LOGLOG. Stratification factor (high vs standard) will be use in **STRATA** statement to get KM estimates by both treatment group and stratum.

Median survival for each treatment group will be obtained along with 95% CIs calculated from PROC LIFETEST output using the method of ([Brookmeyer and Crowley 1982](#)). Kaplan-Meier estimates of the survival function with 95% CIs at specific time points will be summarized. The standard error of the KM estimate will be calculated using Greenwood's formula ([Collett 1994](#)).

Hazard Ratio

Hazard ratio will be estimated by fitting the Cox proportional hazards model using SAS procedure PHREG.

A stratified unadjusted Cox model will be, that is, the MODEL statement will include the treatment group variable as the only covariate and the **STRATA** statement will include stratification variable(s).

Hazard ratio with 2-sided 95% CI will be based on Wald test.

The above survival analyses (ie, log-rank test, KM method and Cox proportional hazards model) do not consider competing risk to be an issue.

Table No.	Title	Population	Standard	In-Text

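### SAP 7.3 lets the covariates of the supportive regression models change after unblinding, and the readable text gives no rule for doing so

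*SAP*

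**What the plan says.** The opening paragraph of SAP 7.3 states that, whatever the type of regression, "the covariates in the final model can differ from what is specified, depending on the unblinded data". Although it stands under the primary endpoint, it names Cox and competing-risks models, which appear only in SAP 7.4, so it must be read as reaching them.

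The models that it makes provisional are these:

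- **Logistic, Day 28 ORR (SAP 7.3.1.2):** "Logistic regression method with both treatment group and baseline GVHD risk status as cofactors in the model". Appendix A describes the same model, "with both treatment and stratification factor specified as an explanatory variable in the CLASS statement". It adds that the model permits adjustment for further covariates, but names none.
- **Cause-specific hazard, NRM (SAP 7.4.3):** a stratified Cox regression "with a cofactor of treatment group will be used to estimate cause-specific hazard ratio (itacitinib vs placebo) and 95% CI".
- **Subdistribution hazard, NRM (SAP 7.4.3):** a stratified Fine-Gray regression "with cofactor of treatment group (itacitinib vs placebo) will be performed".
- **Cox, NRM, FFS and OS (SAP 7.4.2, 7.4.9, 7.4.10):** the hazard ratio "will be calculated, along with its 95% CI, using a stratified Cox model". The covariates come from Appendix A: "A stratified unadjusted Cox model will be, that is, the MODEL statement will include the treatment group variable as the only covariate".

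Parts of SAP 7.4.2, 7.4.3, 7.4.9 and 7.4.10 are blacked out. SAP 9.2 assigns the final analyses to the sponsor.

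**The concern.** The stated trigger for changing a model is the unblinded data. It is not a blinded data review, a convergence failure or a failed model check. Whoever chooses the covariates can therefore already see the treatment effect under each choice. A sensitivity analysis whose form is settled that way gives weak evidence of robustness. A reader of the report could not tell whether covariates were chosen by a neutral rule, which is harmless for error, or in the direction that favours itacitinib. The sentence also does not confine covariates to baseline variables, and it would equally allow risk status to be dropped from the logistic model.

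At stake are one of the three listed sensitivity analyses of Day 28 ORR and the NRM, FFS and OS hazard ratios with their confidence intervals. SAP 3.2 gives endpoints other than the primary and key secondary no multiplicity control and relies on 95% intervals for estimation, so the credibility of those intervals matters.

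**Working it through.** **1. What the sentence reaches.** Day 28 ORR is tested by stratified CMH (SAP 7.2, 7.3.1.1), and so is Month 6 NRM (SAP 7.4.1.1). Neither test has a free covariate. Kaplan-Meier, log-rank and Gray's analyses are not regressions and are also outside it.

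**2. The plan's own figures.** Inputs from SAP 3.3: ORR 68% vs 81% (standard risk) and 44% vs 61% (high risk), strata 50:50, 207 per arm (103.5 per arm and stratum), one-sided 0.025.

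- Difference: 0.5 × 0.13 + 0.5 × 0.17 = 0.15.
- Null variance: 0.25 × (2 × 0.745 × 0.255 + 2 × 0.525 × 0.475)/103.5 = 0.002122, SE 0.04607.
- Alternative variance: 0.25 × (0.3715 + 0.4843)/103.5 = 0.002067, SE 0.04547.
- Power: Φ[(0.15 − 1.96 × 0.04607)/0.04547] = Φ(1.313) = 90.5%, against the stated 90% or so.
- Randomised total: 414/0.95 = 435.8, so 436.

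Both figures reproduce. Neither contains a regression covariate, so locking the covariates changes neither.

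**3. False-positive rate with no true effect.** SAP 7.3 names no covariates, so these inputs are assumed: 1, 3 or 6 independent binary factors, prevalence 0.5, each with odds or hazard ratio 1.5 or 2.0. For scale, SAP 7.3.4 lists 16 subgroup factors. Fourteen remain after removing risk status and the one determined after randomisation. Set-up: 436 subjects, 109 per arm and stratum, control rates from SAP 3.3, significance at z > 1.96. Cox follow-up runs to Day 180 without competing events or dropout.

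| Rule for choosing covariates | Logistic | Cox |
|---|---|---|
| Model as specified | 2.5–2.7% | 2.4–2.7% |
| Neutral (factor p < 0.05, or any imbalance p < 0.10) | 2.2–2.7% | 2.1–3.0% |
| Only imbalances against itacitinib (p < 0.20) | 2.7–3.3% | 2.5–3.5% |
| Most favourable subset, 1 factor (1.5 / 2.0) | 2.9 / 2.9% | 2.7 / 2.9% |
| Most favourable subset, 3 factors (1.5 / 2.0) | 3.2 / 3.8% | 3.7 / 4.5% |
| Most favourable subset, 6 factors (1.5 / 2.0) | 4.2 / 5.2% | 5.5 / 7.4% |

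Monte Carlo margins are ±0.2 to 0.3 points (logistic) and ±0.2 to 0.5 points (Cox). A separate logistic simulation with 414 subjects and log odds ratios of 0.3 to 0.7 gave 2.1–2.5% for the fixed model. For the most favourable subset it gave 2.8–3.4% (3 factors) and 3.2–4.6% (5 factors). A further logistic run with three factors of odds ratio 2.0 gave 4.0%, against about 2.7% as specified. The Cox column has no such cross-check and should be read as indicative.

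**4. What adjustment does to the logistic estimate under the planned effect (factors of strength 2.0, no selection).** Adding three factors moves the mean odds ratio from 2.02 to 2.15 and the mean SE of its log from 0.210 to 0.220. With six factors the odds ratio is 2.26 and the SE 0.230. In z terms:

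- Specified: ln 2.02/0.210 = 3.35
- Three factors: ln 2.15/0.220 = 3.48
- Six factors: ln 2.26/0.230 = 3.55

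Simulated power rises from 91.6% to 93.4% (three factors) and from 91.9% to 94.6% (six factors), gains of 1.8 and 2.7 points. Precision falls. The gain comes from a conditional odds ratio further from 1.

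**The case against.** The strongest reply is that nothing confirmatory depends on these models. This stands in full. The protocol (9.4.2) plans proportion tests, log-rank and Kaplan-Meier for the secondary efficacy endpoints, and the fixed CMH, log-rank and Gray's results would appear beside any adjusted estimate. Those tests do not supply a fixed hazard ratio, however, so the gap is not fully closed.

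Second, the larger error rates need assumed factors and a deliberate search of every subset. That also stands: neutral selection shows no material inflation.

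Third, a reader might infer that SAP 7.3 contradicts Appendix A. It does not. SAP 7.3 is an express override, and Appendix A is the default that it overrides.

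Fourth, a rule might lie under the redactions. That cannot be excluded for the SAP 7.4 subsections, so the statement that no rule is given applies to SAP 7.3 and the readable text only.

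Fifth, sparse data could justify flexibility. For ORR, Appendix A already provides that "the odds ratio should be determined using exact logistic regression" where an exact test has been used. That does not cover Cox or Fine-Gray models, but any such fallback could have its trigger named in advance.

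**Conclusion.** The concern holds in a limited form. SAP 7.3 permits data-driven covariate choice after unblinding in all four regression types, and the readable text sets no limit. Only supportive estimates are exposed. In the logistic model a deliberate most-favourable search over three to six factors raises a nominal 2.5% one-sided error to about 3–5%. The Cox figures are larger but rest on a single set of simulations. All these sizes depend on assumed covariates, because the SAP names none.

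Three stronger inferences are not supported. The family-wise error of 0.025 is not at risk, since both controlled tests are CMH. Covariate adjustment is not biased in itself, since neutral rules did no material harm. An adjusted odds ratio that differs from the 2.02 in SAP 3.3 spoils no planned comparison: that figure serves the CMH sample size and equals the crude (0.72/0.28)/(0.56/0.44). Severity is minor to should-fix.

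**What to change.** 1. Delete the sentence in SAP 7.3.
2. State that the models as written in the SAP are final and will always be reported.
3. Label any other covariate-adjusted model post hoc and show it beside the specified one. If adjustment is wanted as a planned analysis, name its covariates and selection rule in an SAP amendment before unblinding.
4. In Appendix A, state that the sensitivity logistic model contains only treatment and randomisation stratum, and that the CMH odds ratio of SAP 7.3.1.1 is the primary one. This closes the open reference there to other covariates.

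The cost is one deleted sentence and a few added lines, with no change to the sample size, the confirmatory tests or the protocol. The sponsor gives up discretionary adjustment after unblinding and the power gain of about 2 to 3 points shown in step 4, which is not a gain in precision. It can still report such models as post hoc.

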7.3.1. Primary Efficacy Analysis

7.3.1.1. Day 28 Overall Response Rate

The primary efficacy endpoint, ORR at Day 28 (ie, with either a CR, VGPR, or PR at Day 28 assessment or other response assessments within 3 days of Day 28, before start of new anti-GVHD therapy), will be analyzed using a stratified CMH test. Note that the EOT visit must be accounted for in the Day 28 ORR calculation, because when the EOT and Day 28 visits occur at the same time, per protocol, EOT will supersede the Day 28 visit. That is, if the EOT visit occurs when the Day 28 visit is planned, data from the EOT visit will be used in lieu of the Day 28 visit.

Responders ([CIBMTR 2009](#), [Harris et al 2016](#); refer to Protocol Appendix B):

- (CR) Complete response
- (VGPR) Very good partial response
- (PR) Partial response

Non-responders:

- (MR) Mixed response
- (PD) Progression of disease
- (NR) No response
- (NA) Not applicable
- Other
- Missing (primary reason)
 - Death prior to the Day 28 visit
 - Withdrawal from study prior to the Day 28 visit
 - Initiation of new anti-GVHD therapy prior to the Day 28 visit
 - Missing visit

Day 28 ORR will be summarized using descriptive statistics (N, %) by treatment group with 2-sided exact binomial 95% CIs. P-value, mean proportion difference, odds ratio, and 95% Wald confidence limits calculated from stratified CMH test will be also presented.

7.3.1.2. Sensitivity Analyses for Day 28 Overall Response Rate

Sensitivity analyses for Day 28 ORR will consist of the following:

- Stratified CMH test for Day 28 ORR in the full and per-protocol analysis sets
- Logistic regression method with both treatment group and baseline GVHD risk status as cofactors in the model for the efficacy population
- Separate CMH test by baseline GVHD risk status

7.3.2. Duration of Response for Day 28 Responders

The DOR is defined from the time of the first response to the loss of response (ie, either disease progression or death). Responders who did not progress or die after onset of response will be censored, and response will be ended at either study withdrawal, initiation of new anti-GVHD therapy, or last response assessment before or on the cut-off date, whichever is earliest.

Duration of response will be calculated for every responder as well as Day 28 responders.

The DOR for the Day 28 responders will be assessed using the KM method only for subjects who achieve Day 28 response. The KM curves; medians; 1-, 2-, 6-, 12-, 18- and 24-month (equivalently at Days 30, 60, 180, 365, 547, and 730) survival estimates and 95% CIs will be estimated ([Brookmeyer and Crowley 1982](#)). The DOR will be assessed for each treatment group and also by stratum and Day 28 response status.

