### **7.6. Efficacy Assessments**

#### **7.6.1. GVHD Staging and Grading**

Acute GVHD grading will be performed by the investigator on a weekly basis for the first 8 weeks after randomization, then every 28 days thereafter. GVHD staging and grading will also occur on Days 100, 180, and 365 and at the EOT visit.

On-treatment aGVHD grading should be performed relative to the Day 1 assessment.

If subjects withdrew due to reasons other than GVHD progression, then GVHD staging and grading will be assessed at the safety follow-up visit and every 28 days thereafter during survival follow-up until progression of GVHD, start of new anti-GVHD therapy, or death.

Data regarding the quantification of aGVHD symptoms (extent of skin rash, total bilirubin level, volume of diarrhea) should be reported using MAGIC guidelines ([Harris et al 2016](#)); response will be assessed as per CIBMTR modifications to the IBMTR response index as indicated in [Appendix B \(CIBMTR 2009\)](#).

- Skin:
  - Only areas involved with active erythema should be used for determination of body surface area staging based on the rule of nines.
  - A portion of a body area segment may be used for the quantification.
  - Desquamation or fluid-filled bullae should be reported if present, as these findings are the hallmark of Stage 4 skin GVHD.
- Liver:
  - Liver GVHD staging is based solely on total (not conjugated/direct) serum bilirubin levels.

- Liver GVHD manifesting as transaminitis without concomitant elevation in serum bilirubin should be diagnosed when the presence of GVHD is confirmed by liver biopsy (where appropriate) and score it as Stage 0.
- If bilirubin levels were elevated before the diagnosis of GVHD in another target organ and do not increase further, liver GVHD should not be diagnosed in the absence of biopsy confirmation. However, if hyperbilirubinemia develops at the same time or after the onset of GVHD in another target organ, liver GVHD is presumed to be present in the absence of an identified alternative cause.
- Upper GI:
  - Symptoms of concern for upper GI GVHD include anorexia, nausea, vomiting, and dyspepsia, and assessment depends on close attention to caloric intake and symptom reporting.
  - An upper GI endoscopy should be performed whenever possible to confirm upper GI GVHD; however, the diagnosis may be made without biopsy confirmation.

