### Response Definitions:

- CR is defined as CIBMTR score of 0 for the GVHD grading in all evaluable organs. For a response to be scored as CR at day 28 or later, the participant must still be in CR on that day and have had no intervening additional therapy for an earlier progression, partial response (PR) or no response (NR).
- VGPR is defined as:
  - Skin: No rash, or residual erythematous rash involving < 25% of the body surface, without bullae (residual faint erythema and hyperpigmentation do not count)
  - Liver: Total serum bilirubin concentration <2 mg/dL or <25% of baseline at enrollment
  - Gut:
    - Tolerating food or enteral feeding
    - Predominantly formed stools
    - No overt gastrointestinal bleeding or abdominal cramping
    - No more than occasional nausea or vomiting
- Partial response (PR) is defined as improvement in one or more organs involved with GVHD symptoms without progression in others. For a response to be scored as PR at Day 28 or later, the participant must still be in PR on that day and have had no intervening additional therapy for an earlier progression, PR or NR.
- Mixed response (MR) is defined as improvement in one or more organs with deterioration in another organ manifesting symptoms of GVHD or development of symptoms of GVHD in a new organ.
- Progression of disease (PD) is defined as deterioration in at least one organ without any improvement in others.
- No response (NR) is defined as absence of any improvement or progression as defined. Patients receiving secondary therapy (including need to re-escalate steroid dose to  $\geq 2.5$  mg/kg/day of prednisone or methylprednisolone equivalent of 2mg/kg/day), will be classified as nonresponders.

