2.2. Study Objectives and Endpoints

[Table 1](#) presents the study objectives and endpoints.

Table 1: Objectives and Endpoints

Primary Objective	Primary Endpoint
Compare the efficacy of itacitinib in combination with corticosteroids versus placebo in combination with corticosteroids in terms of ORR at Day 28 in subjects with aGVHD.	ORR at Day 28, defined as the proportion of subjects demonstrating a CR, VGPR, or PR.
Key Secondary Objective	Key Secondary Endpoint
Compare the efficacy between treatment cohorts at a subsequent key clinical landmark.	NRM at Month 6, defined as the proportion of subjects who died due to causes other than malignancy relapse at Month 6.
Secondary Objectives	Secondary Endpoints
Compare additional response and longer-term efficacy outcomes between treatment cohorts.	ORR, defined as the proportion of subjects demonstrating a CR, VGPR, or PR at Days 14, 56, and 100.
	NRM at Months 9, 12, and 24.
	DOR for responders will be calculated. The DOR is defined from the time of the onset of response to loss of response. Subjects who died or discontinued will be censored at the death date or the previous assessment.
	TTR, defined as the interval from treatment initiation to first response.
	Relapse rate of malignant and nonmalignant hematologic diseases, defined as the proportion of subjects whose underlying hematologic disease relapses.
	Malignancy relapse-related mortality rate, defined as the proportion of subjects whose malignancy relapses and has a fatal outcome.
	FFS, defined as the proportion of subjects who are still alive, have not relapsed, have not required additional therapy for aGVHD, and have not demonstrated signs or symptoms of cGVHD, at Month 6.
OS, defined as the interval from study enrollment to death due to any cause.	
Assess the incidence and severity of AEs and SAEs.	Clinical safety data (eg, AEs, infections) will be tabulated and listed.
Evaluate the PK of itacitinib when administered in combination with corticosteroids.	C_{max} , C_{min} , t_{max} , AUC, and CL/F.
Evaluate the incidence of secondary graft failure.	Incidence rate of secondary graft failure, defined as > 95% recipient cells any time after engraftment with no signs of relapse, OR retransplantation because of secondary neutropenia ($< 0.5 \times 10^9/L$) and/or thrombocytopenia ($< 20 \times 10^9/L$) within 2 months of transplant.

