7.1. General Considerations

In all efficacy analyses, initiation of new, systemic anti-GVHD therapy includes 2 scenarios:

1) initiation of new anti-GVHD therapy including a higher dose of corticosteroid than that used at Day 1 and 2) initiation of new, systemic anti-GVHD therapy when subjects who were treated with placebo in the treatment phase were re-treated with itacitinib in the retreatment phase.

Initiation of new, systemic anti-GVHD therapy will be considered when defining the following:

1) onset of response and 2) loss of response. When defining responder for Day 28 ORR; overall response at Days 14, 56, 100, and 180; and BOR, the onset of response will be censored by initiation of new, systemic anti-GVHD therapy. Responders who did not have GVHD progression or death after response will be censored at the time of either study withdrawal, initiation of new, systemic anti-GVHD therapy, or the date of last assessment of GVHD before or on the cutoff date, whichever is earliest. In the survival analysis of NRM, all subjects in the analysis set in question without a death due to causes other than malignancy relapse will be censored at either study withdrawal, death due to malignancy relapse, or the date of last contact before or on the cutoff date, whichever is earliest.

Duration of response will be calculated for every subject who has a response in the study; DOR will also be summarized for any subgroups of interest.

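### The main duration-of-response definition has only progression or death as events, so a return to Day 1 staging (NR) or a mixed response (MR) does not end response

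*SAP*

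**What the plan says.** **Endpoint level.** SAP Table 1 (Section 2.2), in the same terms as Protocol Section 2, states: "The DOR is defined from the time of the onset of response to loss of response".

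**Analysis level.** SAP 7.3.2 specifies: "The DOR is defined from the time of the first response to the loss of response (ie, either disease progression or death". Its rule for all remaining responders begins: "Responders who did not progress or die after onset of response will be censored, and response will be ended at either study withdrawal, initiation". The quote is cut there; besides withdrawal, the clock also stops when another GVHD treatment is started or at the final rating up to the data cutoff, and the earliest of these applies. SAP 7.1 has the same structure: "Responders who did not have GVHD progression or death after response will be censored at the time of either study withdrawal". It then names the same two further stopping points. Protocol 9.4.2 also runs DOR to GVHD progression or death.

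**Rating rules.** Protocol 7.6.1: "On-treatment aGVHD grading should be performed relative to the Day 1 assessment"; the same section sends response assessment to Appendix B. Appendix B gives three separate categories below partial response:
- The PD entry, which needs worsening somewhere and improvement nowhere: "Progression of disease (PD) is defined as deterioration in at least one organ without any improvement in others".
- The MR entry, which also extends to organs not affected before: "Mixed response (MR) is defined as improvement in one or more organs with deterioration in another organ manifesting symptoms of GVHD or development of symptoms".
- The NR entry, which is what remains when staging is back at Day 1: "No response (NR) is defined as absence of any improvement or progression as defined".

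**Response rate.** SAP 7.3.1.1 lists MR, PD and NR together as nonresponders at Day 28. SAP 7.4.4 builds ORR at Days 14, 56, 100 and 180 in the same way.

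**Alternatives.** SAP 7.3.3 gives two further DOR calculations for Day 28 responders, both starting at Day 28. Approach 2 counts any organ stage worse than at best response as an event.

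**The concern.** The endpoint tables promise the time until response is lost, but the analysis sections recognise only one of the three nonresponse ratings as a loss. A subject's Day 56 or Day 100 visit can then be nonresponse in the ORR table and still in response in the DOR analysis. DOR is a named secondary endpoint and the main description of durability, and the mismatch runs in one direction, towards longer response. The subjects affected are those whose disease comes back to where it started, or shifts between organs, without becoming uniformly worse than at Day 1.

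**Working it through.** The documents give no DOR rate, median or power, so there is no figure to reproduce. The check applies the rating rules to staged examples.

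**Rule.** Compare each organ stage with Day 1. Improvement in some organ and none worse is PR (CR if all are zero). Improvement in one with worsening in another is MR. Worsening with no improvement is PD. Neither is NR. VGPR was not coded; it does not affect the NR, MR or PD results below.

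**Example subject.** Day 1 is skin Stage 3 and lower GI Stage 1, liver and upper GI 0 (Grade II by Appendix B). For the approach 2 column, the subject is taken to be a Day 28 responder whose best response at or after Day 28 is the one shown.

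| Case | Response reached | Later staging | Rating against Day 1 | Event, SAP 7.3.2 | Event if NR, MR or PD ends response | Event, approach 2 |
|---|---|---|---|---|---|---|
| a | PR (skin 1, GI 0) | skin 3, GI 1 | NR | no | yes | yes |
| b | CR | skin 3, GI 1 | NR | no | yes | yes |
| c | PR (skin 1, GI 0) | skin 1, GI 3 | MR | no | yes | yes |
| d | PR (skin 1, GI 0) | skin 4, GI 1 | PD | yes | yes | yes |
| e | CR | skin 2, GI 1 | PR | no | no | yes |

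Cases a to c are nonresponse for ORR at that visit, yet the subject remains at risk as a responder under 7.3.2. The subject leaves the risk set only at later PD or death, or by censoring at study withdrawal, new anti-GVHD therapy or last assessment.

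**Direction.** The events PD and death are a subset of NR, MR, PD and death, and the censoring times are the same under both rules. A subject's first event under the wider rule therefore falls at or before the first event or censoring under the narrower one. Each duration stays the same or shortens, and some censored durations become events.

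**Coverage of the alternatives.** Approach 2 catches a to e, but only for Day 28 responders and with the clock starting at Day 28. SAP 7.3.2 also calculates DOR for every responder, and that analysis has no counterpart to approach 2.

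**The case against.** Five arguments deserve weight.

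1. *Response does not run on until progression alone.* Correct. Death is an event, and new anti-GVHD therapy, which under SAP 7.1 includes corticosteroids above the Day 1 dose, stops the clock. A relapsing responder who needs such therapy is not carried forward. But that subject leaves by censoring, so the loss itself is still not counted.

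2. *The Day 1 reference is inferred.* Also correct. SAP 7.3.2 names no reference point and does not cite the Appendix B PD category, and Protocol 7.6.1 speaks of grading. Protocol 1.5 and 5.4.3 use progression more loosely for subjects tapering study drug, including when additional systemic therapy is needed. A reader might infer that the plan expressly rules out a return to baseline as an event; it does not. The reading comes from joining sections. However, approach 2 spells out comparison with best response as an alternative, which suggests that the main definition differs. If the broader meaning is intended, the SAP has to say so.

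3. *The SAP did not invent the narrow definition.* It follows Protocol 9.4.2. The inconsistency with the endpoint table is already inside the protocol.

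4. *A flare is not necessarily failure.* Protocol 5.2.3 does not treat a flare during steroid taper as treatment failure if re-escalation stays within the starting dose, and flares through Day 100 are a separate endpoint. Ending DOR at one NR or MR visit is therefore a choice of estimand. That is a good reason to keep the progression-or-death version as a sensitivity analysis. It does not reconcile that version with an endpoint described as time to loss of response.

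5. *Approach 2 already covers the gap.* It does for Day 28 responders, and it also catches case e. It does not cover the all-responder DOR or the main definition.

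**Conclusion.** The point stands as a mismatch between the DOR event rule and both the stated endpoint and the SAP's own list of nonresponse ratings. It rests on reading progression in SAP 7.3.2 as the Appendix B category judged against Day 1.

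The direction is fixed for each subject: the recorded duration can be too long but not too short relative to loss of response. The size cannot be computed, because the documents give neither DOR event rates nor the frequency of NR and MR after response. A shift in the median cannot be derived, and a Kaplan-Meier curve need not fall at every time point, since the risk sets change too.

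Two stronger conclusions are tempting and unsupported. One could count stage combinations and report the share rated PD as a magnitude. Such a count weights profiles by how many permutations they have, with three- and four-organ disease dominating, and says nothing about patients. One could also infer that the treatment comparison is biased. The rule applies to both arms, and the documents contain nothing that shows a differential effect.

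DOR has no multiplicity control (SAP 3.2). The tests of Day 28 ORR and Month 6 NRM are unaffected.

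**What to change.** In SAP 7.1 and 7.3.2:
- Define loss of response as the first assessment after response whose organ staging rates NR, MR or PD against Day 1, that is, no longer CR, VGPR or PR, or death. Name Day 1 as the reference point.
- State that NR assigned solely because of new anti-GVHD therapy follows the existing new-therapy rule. The Appendix B NR entry also classes subjects on secondary therapy as nonresponders; without this sentence, the new event would collide with censoring at new therapy.
- Keep progression or death as a sensitivity analysis.
- Record the change from Protocol 9.4.2 in SAP 10.1, which at present notes only the equivalence of the analysis populations.

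The endpoint tables censor deaths while 7.3.2 counts them as events. That is a separate inconsistency, but the same edit should settle it.

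The cost is wording and reprogramming of one derived variable; response ratings are already scheduled at the treatment visits, so no new data are needed. The reported DOR will be somewhat shorter. Recurrences still rated PR against Day 1, such as case e, will remain visible only through alternate approach 2.
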